8.1.2.12. Group 1A: Day 35: – Post-vaccine Steady-State Ciprofloxacin PK Session

1. Provide a non-dairy breakfast 30 to 60 min prior to dosing; provide a light lunch and a light dinner/snack over the course of the day.
2. Assess vital signs (seated/semi-recumbent blood pressure, heart rate, respiratory rate and temperature).
3. Collect blood sample for ciprofloxacin t=0 concentration determination prior to administration of AM dose of ciprofloxacin.
4. Administer AM dose of ciprofloxacin (500 mg po) following blood sample collection for t=0 concentration determination and record time of administration in the source document and the eCRF; ensure the participant remains semi-recumbent for two hours after dosing and continues with a light activity level throughout the day.
5. Blood samples for ciprofloxacin PK assessment are to be collected at the following time points: 0.25, 0.5, 0.75, 1, 1.5, 2, 2.5, 3, 4, 5, 6, 8, 10 and 12 hours post-dose (± 5 min through hr 4, then ± 15 min thereafter).
6. Administer ciprofloxacin 500 mg po in the clinic after the final 12-hour ciprofloxacin PK sample has been collected and 12 hours after the morning dose (± 30 min).
7. Record concomitant medications.
8. Return ciprofloxacin supply to participant
9. When the participants are discharged from the clinic, they will be reminded:
 - about the diet and activity precautions that must be followed when taking ciprofloxacin (see [Section 5.3](#)).
 - to continue to use the antibiotic e-diary to record the times they take their ciprofloxacin doses each day and to use the reactogenicity e-diary to record any vaccination reactions, if applicable, see [Section 8.3.5.1](#) (Participant e-diary).

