Blood and urine samples for safety clinical laboratory testing (hematology, serum chemistry, urinalysis) will be collected at Screening and Day 51 as well as at the EWV if the EWV occurs before Day 51. Refer to [Table 10](#) for the list of analytes for hematology, serum chemistry and urinalyses. The laboratory test results will be evaluated against the FDA toxicity grading scale provided in [Table 13](#) of [Appendix A](#).

In addition, blood samples for TSH & autoantibody assessment of ANA, RF and anti-dsDNA will be taken at Day 1 after randomization, Day 51 or EWV or an unscheduled visit if the participant has received at least one dose of vaccine and at the time of safety follow-up phone contact(s) if warranted from participant report(s) of a potential AESI (see [Table 10](#) for the list of analytes for autoantibody testing). These samples will be shipped to the central laboratory and will be banked; testing for TSH and ANA, RF and anti-dsDNA autoantibodies will be performed only if medically indicated (as per PI's discretion based on a report of a potential AESI).

Instructions for the collection, processing, storage, and shipment of laboratory samples will be provided separately in the Laboratory Manual.

It is the PI's responsibility to review the results of all screening and safety laboratory tests (including unscheduled lab tests) as they become available, initially for the assessment of study eligibility and subsequently for the safety monitoring of participants. Review of the laboratory report must be documented.

For each abnormal laboratory test result, the PI needs to ascertain if this is a clinically significant change from screening level for that individual participant. This determination, however, does not necessarily need to be made the first time an abnormal value is observed. The PI may repeat the laboratory test and/or request additional tests to verify the results of the original laboratory tests. The PI (or designee) will inform the MM of any unscheduled clinical laboratory testing, including but not limited to confirmatory testing of laboratory samples, with the exception that notification is not required for confirmatory testing for pregnancy, HCV, and HIV.

AV7909 Anthrax Vaccine
 IND 014451
 Protocol EBS.AVA.210, Version 3.0 (28 October 2019)

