10.6.4. Vital Signs

Vital signs data will be tabulated by visit and treatment group and listed by individual participant. Observed values and changes from baseline in vital signs will be summarized descriptively (n, mean, median, standard deviation, minimum, and maximum; incidence of abnormality according to highest toxicity grade). Baseline is defined as the last measurement before the first IP administration. In listings, vital sign abnormalities associated with a severity grade based on the toxicity grading criteria (refer to [Table 12](#) in [Appendix A](#)) will be flagged: Grade 1 = mild, Grade 2 = moderate, Grade 3 = severe, and Grade 4 = potentially life-threatening.

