### 3.4 Analysis Time Points

Participant visits occur on protocol-specified days with associated visit windows. The schedule may shift by  $\pm 1$  day at the following visits:

- Day 23 visit of the second vaccination for all participants.
- Day 37 visit of TNA assessment for Group 1, 2B, and 3. There is no shifting flexibility for Group 2A at this visit as PK assessment schedule at Day 38.
- Day 51 of final study visit for all participants.

If not otherwise specified, for the purposes of analysis, the analysis visits will be assigned as provided in **Table 2** for vaccination, immunogenicity (TNA) testing, clinical laboratory data,

vital signs, and physical examinations. Data at unscheduled visits will not be presented in the by-visit summary analyses but will be included in the summary tables by maximum toxicity grade or abnormality when applicable, and in data listings.

**Table 2 Analysis Windows for Vaccination, Immunogenicity (TNA) Testing, Clinical Laboratory Data, Vital Signs, and Physical Examinations**

Analysis Visit	Nominal Day	Lower Limit of Study Day	Upper Limit of Study Day
Baseline	NA	-28	Prior to the first exposure to any study treatment
Day 1	1	1	1
Day 8	8	8	8
Day 23	23	22	24
Day 37	37	36 for Group 1, 2B, and 3, 37 for Group 2A	38 for Group 1, 2B, and 3, 37 for Group 2A
Day 51	51	50	52

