### 3.5 Definition of Baseline

For all analyses, the baseline value is defined as the last non-missing value prior to the first dose of any study treatment.

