### **8.3 Vital Signs**

Vital sign data will be assigned a toxicity grade (Grade 1=mild through Grade 4=potentially life-threatening) according to Protocol EBS.AVA.210, **Table 12**.

Vital signs data will be summarized as follows:

- Observed values and changes from baseline by study visit and treatment group.
- Shift from baseline according to toxicity grading criteria grade (Grade 0, Grade 1-4) (number and percentages) by study visit and treatment group. Grade 0 includes all values not meeting criteria for toxicity of at least Grade 1.

All vital sign records will be provided in the subject data listings. This listing will include all results that are collected throughout the study for the analyte of interest, with all applicable severity grades displayed.

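### SAP Table 2 gives no analysis visit to the early withdrawal visit or to vital signs on Days 31/35 (Group 1A) and 32/38 (Group 2A), and SAP 8.3 omits the protocol's highest-grade vital-sign summary

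*SAP*

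**What the plan says.** **Visit assignment.** SAP 3.4 states: "If not otherwise specified, for the purposes of analysis, the analysis visits will be assigned as provided in" Table 2, for vaccination, TNA, laboratory, vital-sign and examination data alike. The rows are Baseline, Day 1, Day 8 (that day only), Day 23 (22 to 24), Day 37 and Day 51 (50 to 52). The lower limit for Day 37 is "36 for Group 1, 2B, and 3, 37 for Group 2A"; the upper limit is 38, or 37 for Group 2A. On other data SAP 3.4 says: "Data at unscheduled visits will not be presented in the by-visit summary analyses but will be included in the summary tables by maximum toxicity grade", where applicable, and in listings. Neither SAP 3.4 nor SAP 3.6 mentions the EWV.

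**Collection.** Protocol 8.3.2 says that safety laboratory samples "will be collected at Screening and Day 51 as well as at the EWV if the EWV occurs before Day 51". Protocol 8.1.8 adds vital signs and a complete examination at the EWV. The visit steps for Group 1A Days 31 and 35 and Group 2A Days 32 and 38 each call for vital signs. Protocol 8.3.4 excludes Day 37.

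**Reporting.** Protocol 10.6.4 promises, for vital signs, descriptive summaries and "incidence of abnormality according to highest toxicity grade". SAP 8.3 has two vital-sign tables. One is "Observed values and changes from baseline by study visit and treatment group"; the other is a grade shift, also by visit. SAP 8.4 tabulates examination findings by visit. SAP 8.2 has by-visit laboratory tables, a table of highest post-baseline grade and a summary of Grade 3 or higher results.

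**The concern.** Table 2 controls entry to every by-visit safety table, and for vital signs and examinations the SAP specifies no other kind of table. A scheduled record without a row therefore goes to a listing, where no incidence or group comparison is reported.

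Two kinds of record are caught. The first is the vital signs at the PK sessions after both vaccinations. They bear on the secondary objective of assessing the safety of giving antibiotic and vaccine together. The second is the EWV, which the protocol treats as the alternative to Day 51. For a participant who attends an EWV instead of Day 51, it holds the only planned post-baseline laboratory set, and incidence of laboratory abnormalities is a secondary endpoint.

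SAP 3.4 sends unscheduled data to maximum-grade tables, but the vital-sign table that would receive them is the one SAP 8.3 leaves out.

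**Working it through.** There is no stated figure to reproduce. The check maps each scheduled vital-sign day, and each possible EWV day, to the Table 2 windows.

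**1. PK-session vital signs** (days from protocol 4.1.1 and 4.1.3; windows from SAP Table 2)

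| Group | Day | Table 2 row |
|---|---|---|
| 1A | 4 | Baseline |
| 1A | 8 | Day 8 |
| 1A | 31 | none |
| 1A | 35 | none |
| 2A | 2 | Baseline |
| 2A | 8 | Day 8 |
| 2A | 32 | none |
| 2A | 38 | none (Day 37 window is 37 only) |

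Days 4 and 2 count as baseline because vital signs are step 2 and the first dose is step 4 of those visits, and "the baseline value is defined as the last non-missing value prior to the first dose of any study treatment" (SAP 3.5).

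Planned size is 40 in each PK group.
- All PK-session sets: 4 sessions x (40 + 40) = 320.
- Sets with no row: 2 sessions x (40 + 40) = 160, half of the total.
- Of these, on antibiotic: Days 35 and 38 only, 1 x 80 = 80.

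The other 80, on Days 31 and 32, precede the first dose of the third course. The second course ends on Day 24, and vital signs again come before dosing in the visit steps.

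**2. EWV days inside a window** (study days from first treatment to Day 52)

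| Group | Possible days | Inside a window | Outside |
|---|---|---|---|
| 1A, 1B | 4 to 52 = 49 | 1 + 3 + 3 + 3 = 10 | 39 |
| 2A | 2 to 52 = 51 | 1 + 3 + 1 + 3 = 8 | 43 |
| 2B | 2 to 52 = 51 | 10 | 41 |
| 3 | 8 to 52 = 45 | 10 | 35 |

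These count calendar days, not participants. For one type of withdrawal the gap is built in. Under protocol 6.1.4, Group 1 or 2 participants whom illness or fever keeps from vaccination 1 stop antibiotic, are withdrawn, and return for the EWV 7 days later. A stop between Day 2 and Day 8 puts that visit between Day 2 + 7 = 9 and Day 8 + 7 = 15, where Table 2 has no row. They have taken antibiotic, so they are in the Safety Population.

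**3. Where an off-window EWV record goes**

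| Data | By-visit table | Other table | Listing |
|---|---|---|---|
| Graded laboratory analytes | no | yes (SAP 8.2 highest grade) | yes |
| Ungraded analytes, e.g. hematocrit, RBC count, monocytes | no | none specified | yes |
| Vital signs | no | none (SAP 8.3) | yes |
| Examination findings | no | none (SAP 8.4) | yes |

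Vital signs on Days 31/35 and 32/38 follow the same path as the vital-sign line.

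**The case against.** **The loss is limited, and much of it is caught elsewhere.** This stands. Graded laboratory results reach SAP 8.2. Under protocol 8.3.4 and 9.2.3, clinically significant vital-sign changes, and Grade 3 or higher values confirmed in two of three readings, are recorded as AEs. What goes unsummarised is mainly Grade 1 and 2 vital signs, descriptive changes, ungraded laboratory results and examination findings. These tables carry no hypothesis test.

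**The EWV can be treated as unscheduled.** The protocol's schedule tables put the two in one column, so this is a plausible reading. It helps graded laboratory data only: SAP 8.3 has no maximum-grade table to receive the vital signs, and SAP 8.4 has no table across visits. Nor does it fit the PK sessions, which are scheduled.

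**A programmer might tabulate by collected visit name anyway.** Possibly, but SAP 8.3 specifies nothing different from Table 2, so Table 2 governs. Narrow windows are a legitimate choice, and the Day 37 row is needed for TNA.

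**Stronger readings that a reader might infer, and that the documents do not support:**
- That all PK-day vital signs are lost. Days 2, 4 and 8 have rows.
- That all 160 sets were taken on antibiotic. Half precede the restart of dosing.
- That the 25% allowance gives an EWV count (0.25 x 70 = 17.5 per group). The protocol synopsis describes it as exclusion from the immunogenicity population. Many reasons for exclusion, such as a detectable Day 1 TNA or an out-of-window sample, do not stop a participant attending Day 51.
- That participants who stop for an AE generally vanish from Day 51. Protocol 7.3 and 7.3.1 encourage those already vaccinated to attend the remaining safety visits; the EWV is for those who decline.

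**Conclusion.** The point holds as a gap between protocol and SAP in descriptive safety reporting. Table 2 omits the EWV and four scheduled PK-session days for vital signs, and SAP 8.3 omits a summary promised in protocol 10.6.4. Together these leave about 160 of 320 planned PK-session vital-sign sets in listings only, about 80 of them taken on antibiotic. The same applies to the vital signs and examinations of any EWV outside the windows, whose laboratory results also miss the change and shift tables.

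The 160 assumes 40 participants in each PK group, full attendance and sessions on their nominal days. The documents give no EWV rate, so the number of participants affected through the EWV cannot be stated. Primary PK and immunogenicity tests are unaffected. The change is worth making because it is cheap and alters what the safety tables report.

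**What to change.** 1. In SAP 8.3, restore the vital-sign table of highest post-baseline toxicity grade by treatment group, including EWV and unscheduled records. This alone brings the graded values from all the affected visits into a summary.
2. In Table 2, add vital-sign rows for Days 31 and 35 (Group 1A) and Days 32 and 38 (Group 2A).
3. Rename the last safety row Day 51/EWV and assign to it only the final-visit or EWV laboratory, vital-sign and examination record, whatever its study day. Footnote that EWV days vary. Leave the vaccination and TNA windows as they are.

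Step 3 must not extend to every post-treatment record. SAP 3.6 takes the highest-graded of several records in a window, so a row holding all of them would show the worst case of the whole study under a Day 51 label.

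The cost is SAP wording and programming of data already collected. The downside is that the Day 51/EWV row mixes study days, and an EWV may precede Day 51 by several weeks.

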### 3.5 Definition of Baseline

For all analyses, the baseline value is defined as the last non-missing value prior to the first dose of any study treatment.

### 3.6 Selection of Data in the Event of Multiple Records in an Analysis Window

For clinical laboratory data, vital signs, and physical examinations, if multiple valid non-missing observations exist in an analysis window for a specific visit, a single value will be chosen in the by-visit summary analyses based on the following rules:

- For baseline, the last available record prior to the date and time of the first vaccination will be selected.
- For post baseline visits,
  - if the analysis values are numeric and the toxicity grades are available, the record with the highest toxicity grade will be selected;
  - if the analysis values are numeric and the toxicity grades are identical or not available, the average (arithmetic mean) will be used;
  - if the analysis values are categorical, the most conservative value will be selected (e.g., abnormal will be selected over normal).

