Investigational sites will be automatically notified of any Grade 3 or higher laboratory abnormalities. For any Grade 3 or higher laboratory result, the test will be repeated as soon as possible by the central lab using the same blood sample to confirm the result. The PI or designee must request the participant return to the clinic for an unscheduled visit for an assessment of clinical status. The decision to redraw laboratory tests will be made by the PI (with notification to the MM) and/or MM and will be based on the type and severity of the laboratory abnormality and the clinical status of the participant. Any Grade 3 or higher neutropenia or lymphopenia must be evaluated with an unscheduled repeat complete blood count (CBC) approximately 72 hours after the initial specimen was drawn.

If the original (retested sample) or repeat laboratory value is Grade 3 or higher or determined by the PI to be a clinically significant change from baseline for that participant, this will be considered an AE and will be recorded on the AE eCRF. Any other clinical laboratory abnormalities must also be reported as AEs if considered by the PI to be a clinically significant change from baseline. If an abnormal laboratory test result is a sign of a disease or syndrome, the disease or syndrome will be recorded as the AE/SAE and not the abnormal laboratory result. Clinical laboratory abnormalities may trigger individual participant or study halting rules (see [Section 7.1](#) and [Section 7.3](#)) and may require discontinuation of treatment.

Table 10: Screening/Safety Clinical Laboratory Tests

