8.3.4. Vital Signs

Vital signs including seated/semi-recumbent systolic and diastolic blood pressure, heart rate, respiration rate, and temperature will be obtained at Screening and each subsequent clinic visit through Day 51/EWV (except at AM and PM clinic visits for groups 1A and 2A, and at Day 37 for all groups), including unscheduled visits. Height and weight will only be recorded at Screening. On vaccination days (Days 8 and 23), vital signs will be assessed prior to vaccination and at 30 ± 5 minutes post-vaccination.

All vital sign abnormalities determined by the PI or designee to be a clinically significant change from baseline for that participant should be recorded as AEs. Grade 3 or higher vital signs will be repeated twice to verify that the severity is a Grade 3 or higher. If two of the three assessments are Grade 3 or higher, the vital sign should be reported as a Grade 3 or higher abnormality. Vital sign abnormalities may trigger individual participant or study halting rules (refer to [Section 7](#)).

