9.2.3. Eliciting Adverse Events from Other Safety Assessments

Clinical observations during safety evaluations (ie, PEs, vital signs, clinical laboratory tests) determined by the PI or designee to be abnormal and to represent a clinically significant change from baseline must be reported on the AE eCRF regardless of causal association with the IP. This includes any new observation presenting after the dose of IP (either antibiotic or AV7909) or deterioration of baseline condition (ie, increased severity/frequency) after the first vaccination through Day 51 or EWV. If there is any doubt as to whether a clinical observation is an AE, the event will be considered an AE and recorded on the AE eCRF. Additionally, certain types of observations must be reported by the PI or designee as AEs, as follows (refer to the listed sections below for details on retesting and repeat testing requirements associated with this reporting where applicable):

- Following the dose of any IP, all Grade 3 or higher clinical laboratory abnormalities (sample retested and, if needed, test repeated), unless covered under a disease or syndrome that is already reported as an AE; refer to [Section 8.3.2](#) for details.
- Following the first dose of any IP, all vital sign abnormalities found to be Grade 3 or higher in two out of three assessments (original plus two repeats); refer to [Section 8.3.4](#) for details.

Additionally, while reactogenicity from the e-diary will not be duplicated in AE reporting, the PI or designee will record as AEs any e-diary reactogenicity that is serious, results in

AV7909 Anthrax Vaccine
IND 014451
Protocol EBS.AVA.210, Version 3.0 (28 October 2019)

discontinuation of IP or withdrawal from the study, or remains unresolved as of Day 51/EWV (refer to [Section 8.3.5.1](#)).

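### SAP 3.6 tabulates the highest of repeated vital-sign readings, whereas protocol 8.3.4 calls for two of three readings at Grade 3 or higher, so an unconfirmed reading can appear as Grade 3 in the by-visit tables

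*SAP*

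**What the plan says.** Protocol 8.3.4 sets the confirmation procedure. The trigger is: "Grade 3 or higher vital signs will be repeated twice to verify that the severity is a Grade 3 or higher". The threshold follows: "If two of the three assessments are Grade 3 or higher, the vital sign should be reported as a Grade 3 or higher abnormality". Protocol 9.2.3 carries the same threshold into adverse event recording, which covers "all vital sign abnormalities found to be Grade 3 or higher in two out of three assessments (original plus two repeats").

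SAP 3.6 decides which record enters the by-visit summaries. Its scope is: "For clinical laboratory data, vital signs, and physical examinations, if multiple valid non-missing observations exist in an analysis window for a specific visit". For post-baseline visits the first rule is: "if the analysis values are numeric and the toxicity grades are available, the record with the highest toxicity grade will be selected". At baseline it takes the last record instead.

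SAP 8.3 makes that first rule operative, because "Vital sign data will be assigned a toxicity grade". It then plans by-visit summaries of values and changes, and this table: "Shift from baseline according to toxicity grading criteria grade (Grade 0, Grade 1-4) (number and percentages) by study visit and treatment group".

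SAP 2.2.4.4 refers the reader to protocol 8.3.4 for details of vital signs. It announces no departure from it. No section of the SAP applies the two-of-three rule to the tables.

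**The concern.** The protocol takes two extra readings so that a chance high or low reading is not reported as Grade 3. The SAP's selection rule discards that information when it builds the by-visit tables. The grade shown for a participant at a visit can then differ from the grade that the protocol says to report for the same set of readings.

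At stake is agreement between two parts of the safety report. A reader comparing the vital-sign shift table with the adverse event listing could find Grade 3 readings with no matching event and no explanation. The asymmetry in SAP 3.6 adds to this: the last record is used at baseline and the highest-graded record afterwards, so an isolated extreme reading counts towards worsening but need not count at baseline.

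**Working it through.** The plan states no figure to reproduce. The check applies both rules to the same readings.

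**Inputs.** Repeat trigger and two-of-three threshold: protocol 8.3.4. Selection rule: SAP 3.6. Systolic cut-offs, protocol Appendix A, Table 12: Grade 1 is 141–150, Grade 2 is 151–155 and Grade 3 is above 155 mmHg. Visit windows: SAP Table 2.

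**Rules.** Let g1, g2 and g3 be the grades of the first reading and its two repeats.

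- SAP 3.6: tabulated grade = max(g1, g2, g3).
- Protocol 8.3.4: Grade 3 or higher when at least two of g1, g2, g3 are 3 or higher.

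Repeats are taken only when g1 ≥ 3. Hence max(g1, g2, g3) ≥ 3 in every set of three, and under SAP 3.6 no pair of repeats can lower the tabulated grade below 3.

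**Examples (systolic, mmHg).**

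| Readings | Grades | SAP 3.6 | Protocol 8.3.4 | Median and its grade |
|---|---|---|---|---|
| 157, 150, 148 | 3, 1, 1 | Grade 3 | not Grade 3 | 150, Grade 1 |
| 158, 138, 136 | 3, 0, 0 | Grade 3 | not Grade 3 | 138, Grade 0 |
| 157, 156, 148 | 3, 3, 1 | Grade 3 | Grade 3 | 156, Grade 3 |

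The rules disagree in the first two rows. The median agrees with the protocol in all three, because the median of three values passes a one-directional cut-off exactly when at least two of them do.

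The selected record also supplies the value. In the first row, 157 rather than 150 goes into the by-visit mean and change from baseline.

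**Vaccination days.** Protocol 8.3.4 requires vital signs before vaccination and about 30 minutes after it on Days 8 and 23. SAP Table 2 has one window for each of these visits, and SAP 3.6 does not separate the two time points. The highest-grade rule could therefore pick a pre-vaccination reading for the visit, and more than three readings may compete.

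**Size.** The documents give no confirmation rate. As an assumption, let each repeat be Grade 3 or higher with probability q, independently, given a Grade 3 first reading. The share of tabulated Grade 3 sets that fail the protocol rule is then (1 − q)²:

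| q | 0.1 | 0.3 | 0.5 | 0.7 | 0.9 |
|---|---|---|---|---|---|
| (1 − q)² | 81% | 49% | 25% | 9% | 1% |

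The range is too wide to support any single inflation figure. For scale, one participant in a planned group of about 70 is 1/70 = 1.4%.

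**The case against.** The strongest reply has four parts.

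- **The protocol's analysis section also speaks of the highest grade.** Protocol 10.6.4 plans vital-sign abnormality by highest toxicity grade, and 8.3.4 can be read as an instruction to sites, not a tabulation rule. This does not settle the matter. Section 10.6.4 does not say how three readings of one sign become one grade, whereas 8.3.4 says when that sign is to be reported as Grade 3 or higher. It is fair to add that 8.3.4 does not use the word only; that reading rests on its stated purpose of verification.
- **Data capture may prevent the problem.** Under SAP 3.8 the investigator or designee grades vital signs, so a site could enter one adjudicated grade, and SAP 3.6 covers valid records without defining valid. This stands as a condition on the conclusion. Neither document says that one grade is entered or that an unconfirmed reading is invalid.
- **Taking the worst value is conservative and treats all groups alike.** That is true, and it limits the harm. It does not make the tables agree with the protocol.
- **Little depends on these tables.** Vital signs are not among the listed secondary safety endpoints, no safety hypothesis is tested, and SAP 8.3 lists every vital-sign record with its grade. This stands and is why the point is minor.

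A reader might also infer that laboratory results have the same conflict. The documents do not support that. Protocol 8.3.2 has no two-of-three rule: a Grade 3 or higher result on either the retested sample or the repeat test is enough for an adverse event, and SAP 3.4 keeps unscheduled-visit data out of the by-visit summaries.

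**Conclusion.** Wrong as written, of minor severity. SAP 3.6 and protocol 8.3.4 give different grades to the same readings whenever a Grade 3 first reading is not confirmed. The effect is confined to the by-visit vital-sign summaries and the grade-shift table of SAP 8.3.

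The conclusion assumes that the readings fall in the same visit window and are stored as separate, valid, graded records. The number of participants affected cannot be estimated from the documents.

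A reader might infer that the confirmation step has no effect on anything reported. That goes too far: protocol 9.2.3 applies two-of-three to adverse event recording, so the adverse event tables follow the confirmed rule. Nor do the documents support a statement that Grade 3 counts will be inflated by a particular factor, or that a false safety signal will follow.

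**What to change.** Add a rule to SAP 3.6, with a cross-reference in 8.3. For vital signs repeated under protocol 8.3.4, first derive one value and one grade per vital sign, visit and time point by the two-of-three rule, for example the median of the three readings and its grade. Keep pre- and post-vaccination readings separate on Days 8 and 23. Leave Grade 4 criteria that are defined by an event (such as an emergency visit or intubation in Table 12) as recorded. Apply any highest-grade selection only after this step. List all readings and flag the unconfirmed ones.

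The median matches the two-of-three rule in one direction at a time. Signs graded at both ends, such as heart rate and systolic pressure, should therefore be assessed separately for high and low values.

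The cost is a short addition to the SAP and its programming. No new data are needed, and isolated extreme readings remain visible in the listings. The data management team should confirm how repeats are entered, since that decides whether the discrepancy arises in practice.
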